6.2. Pretreatment Assessments

6.2.1. Screening Visit

Subjects will be screened within 30 days before Day 1 Visit to determine eligibility for participation in the study. The following will be performed and documented at screening:

- Obtain written informed consent
- Obtain medical history including history of HIV-1 disease-related events, substance use, family history of cardiovascular disease (i.e. myocardial infarction, stroke, peripheral vascular/arterial disease, and/or angina) and prior medications within 30 days of the Screening Visit
- Complete physical examination (urogenital/anorectal exams will be performed at the discretion of the Investigator)
- Vital signs measurement (blood pressure, pulse, respiration rate and temperature) and weight
- 12-lead ECG performed supine
- Height
- Blood sample collection for the following laboratory analyses:
 - Serum pregnancy test (females of childbearing potential only). If the test is positive, the subject will not be enrolled.
 - FSH test is required for female subjects who have stopped menstruating for > 12 months but do not have documentation of ovarian hormonal failure.

- Chemistry profile: alkaline phosphatase, AST, ALT, GGT, total bilirubin, direct and indirect bilirubin, total protein, albumin, LDH, CPK, bicarbonate, BUN, calcium, chloride, creatinine, glucose, phosphorus, magnesium, potassium, sodium, uric acid, PT/INR, amylase (reflex lipase testing is performed in subjects with total amylase $> 1.5 \times \text{ULN}$) and parathyroid hormone (PTH)
 - Sample should be drawn prior to hemodialysis
 - Timing of draw and timing of hemodialysis should be recorded
- Estimated GFR according to the Cockcroft-Gault formula for creatinine clearance:

Male:
$$\frac{(140 - \text{age in years}) \times (\text{wt in kg})}{72 \times (\text{serum creatinine in mg/dL})} = \text{CL}_{\text{cr}} \text{ (mL/min)}$$

Female:
$$\frac{(140 - \text{age in years}) \times (\text{wt in kg}) \times 0.85}{72 \times (\text{serum creatinine in mg/dL})} = \text{CL}_{\text{cr}} \text{ (mL/min)}$$
- Hematology profile: complete blood count (CBC) with differential and platelet count
- CD4+ T cell count
- Plasma HIV-1 RNA (Taqman v2.0)
- Hepatitis B virus surface antigen serology (HBsAg)
- Hepatitis C virus (HCVAb) serology. If the antibody test result is positive, HCV RNA test will be performed to confirm HCV viremia.

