5.2. Baseline Disease Characteristics

The following baseline disease characteristics collected at enrollment will be summarized:

- Mode of infection (HIV risk factors)
- HIV disease status at study entry
- HCV antibody status at study entry
- Medical history at study entry: Type I or II diabetes (Yes/No), cardiovascular disease (Yes/No), hypertension (Yes/No), and hyperlipidemia (Yes/No) (see [Appendix 7](#) for details)
- Smoking status at study entry: (a) Never Smoked, (b) Former Smoker, and (c) Current Smoker (see [Appendix 7](#) for details)
- Duration of hemodialysis at study entry (years)
- Pre-switch ARV categories: (a) Containing TDF, (b) Containing ABC, and (c) Containing Neither
- Pre-switch ARV categories: (a) Containing 3TC, (b) Containing ABC, (c) Containing TDF, (d) Containing FTC
- Pre-switch ARV 3rd Agent Category: (a) INSTI, (b) PI, (c) NNRTI, (d) CCR5 Antagonist

The following baseline disease characteristics collected prior to E/C/F/TAF administration and prior to B/F/TAF administration will be summarized for the E/C/F/TAF Safety Analysis Set and the B/F/TAF Safety Analysis Set, respectively:

- HIV-1 RNA categories (copies/mL): (a) < 50 and (b) ≥ 50
- CD4 cell count (/µL)
- CD4 cell count categories (/µL): (a) < 50, (b) ≥ 50 to < 200, (c) ≥ 200 to < 350, (d) ≥ 350 to < 500, and (e) ≥ 500

- CD4%
- eGFR_{CG} (mL/min)

No inferential statistics will be provided.

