5.3. Medical History

Subjects' answers to the following questions prespecified on the Medical History CRF will be listed:

- Does the Subject have diabetes? (Type I or II)
- Have any first-degree relatives experienced MI or stroke before the age of 50?

In addition, subjects' kidney transplant registration status collected by the Transplant History CRF will be listed.

General medical history data will be collected at screening and listed only. General medical history data will be coded using the current version of Medical Dictionary for Regulatory Activities (MedDRA).

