7) Please note, “Not Permitted”, “Unknown”, or missing categories will be excluded for percentage calculation. Except for Mode of infection (HIV Risk Factors), where “Unknown” will be included for percentage calculation, since a subject may fit more than 1 HIV risk factors, therefore percentage may add to more than 100%.

Subjects with Race “Not Permitted” will also be excluded to define Race subgroup (ie, black vs. nonblack) for efficacy subgroup analysis.

8) Baseline disease characteristics

Baseline disease characteristics in Section 5.2 will be summarized for both the E/C/F/TAF Safety Analysis Set and the B/F/TAF Safety Analysis Set. Baseline disease characteristics collected at enrollment include mode of infection, HIV disease status, HCV antibody status, medical history (including Type I or II diabetes, cardiovascular disease, hypertension, hyperlipidemia), smoking status, duration of hemodialysis, and pre-switch ARVs. These characteristics are defined prior to the first dose of E/C/F/TAF.

The following baseline characteristics will be re-defined for the B/F/TAF summary:

- HIV-1 RNA categories (copies/mL): (a) < 50 and (b) ≥ 50
- CD4 cell count (/µL)
- CD4 cell count categories (/µL): (a) < 50, (b) ≥ 50 to < 200, (c) ≥ 200 to < 350, (d) ≥ 350 to < 500, and (e) ≥ 500
- CD4%
- eGFR_{CG} (mL/min)

9) Medical history of interest at study entry

Medical history of diabetes, hypertension, cardiovascular disease, and hyperlipidemia will be summarized at study entry (E/C/F/TAF baseline) as baseline disease characteristics. A subject who had medical history of one of these diseases is a subject who experienced at least one selected medical history reported in the Medical History eCRF, including keywords as below.

Hypertension	Diabetes	Cardiovascular Disease	Hyperlipidemia
HYPERTENSION	DIABETES	CEREBRAL VASCULAR ACCIDENT	HYPERLIPIDEMIA
HIGH BLOOD PRESSURE	DIABETIC	CEREBROVASCULAR ACCIDENT	DYSLIPIDEMIA
		MYOCARDIAL INFARCTION	HYPERCHOLESTEREMIA
		CONGESTIVE HEART FAILURE	HYPERCHOLESTOLEMIA
		CORONARY ARTERY DISEASE	HIGH CHOLESTEROL
		CORONARY ARTERY CALCIFICATION	HIGH TRIGLYCERIDES
		PERIPHERAL VASCULAR DISEASE	ELEVATED CHOLESTEROL
		CARDIOMYOPATHY	HYPERGLYCEMIA
		HEART DISEASE	
		TRANSIENT ESCHIMIC ATTACK	
		AGINA	
		ARTERY BLOCKAGE	
		CARDIOVASCULAR DISEASE	

In addition, subject who experienced hypertension before starting study drug according to Adverse Event eCRF with reported term includes the key word “HYPERTENSION”.

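### The keyword lists in SAP Appendix 7 item 9 can misclassify baseline cardiovascular disease and hyperlipidemia in both directions

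*SAP*

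**What the plan says.** SAP 5.2 includes among the baseline disease characteristics "Medical history at study entry: Type I or II diabetes (Yes/No), cardiovascular disease (Yes/No), hypertension (Yes/No), and hyperlipidemia (Yes/No". It refers to Appendix 7 for the derivation, and item 8 of that appendix says the section 5.2 characteristics are summarized for both the E/C/F/TAF and the B/F/TAF Safety Analysis Sets.

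Item 9 of Appendix 7 supplies the rule. A subject is positive if he or she "experienced at least one selected medical history reported in the Medical History eCRF, including keywords as below", and a four-column table of keywords follows. The entries that matter here are:

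- **Cardiovascular disease:** "TRANSIENT ESCHIMIC ATTACK" and AGINA are listed, with no correctly spelled counterpart of either. The nearest entries to stroke are "CEREBROVASCULAR ACCIDENT" and a similar phrase beginning CEREBRAL VASCULAR.
- **Hyperlipidemia:** "HYPERCHOLESTEREMIA" and HYPERCHOLESTOLEMIA are listed; HYPERCHOLESTEROLEMIA is not. HYPERGLYCEMIA is in the same column.

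A coded source exists. SAP 5.3 states: "General medical history data will be coded using the current version of Medical Dictionary for Regulatory Activities". Item 9 does not use those codes, and it provides for no medical review of matches or non-matches. For on-study events, Appendices 4 and 5 instead use prespecified preferred-term lists that medical monitors have reviewed.

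**The concern.** A programmer who follows item 9 literally will miss correctly spelled forms of common cardiovascular and lipid diagnoses, and will count some records that are neither. The table would then print wrong counts for two of the four medical-history rows wherever such terms occur in the data.

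At stake is the description of the population. In a small single-arm study of dialysis patients, baseline cardiovascular and lipid history is part of the context in which a reader takes the safety results. There is also an inconsistency of definition. Baseline cardiovascular history rests on free text, while on-study cardiovascular and cerebrovascular events rest on MedDRA queries for myocardial infarction, other ischemic heart disease and ischemic central nervous system vascular conditions (Appendix 4). The same diagnosis could be recognized on study and missed at baseline.

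**Working it through.** The plan states no count for these histories, so there is no figure to reproduce. The check is a string test of the keywords, followed by the size of one misclassification.

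**Inputs**

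- Keywords: SAP Appendix 7 item 9, cardiovascular and hyperlipidemia columns.
- Matching rule: item 9 asks for records that include a keyword. I read this as a case-insensitive substring search; item 9 does not specify case or whole-word matching.
- Denominator: 55 treated subjects (Protocol 1.2.5, interim Week 48 safety results, 18 of 55; also the disposition mock, SAP Appendix Table 1).

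**Step 1. Terms that should match**

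| Reported term | Matching keyword |
|---|---|
| ANGINA, ANGINA PECTORIS, UNSTABLE ANGINA | none |
| TRANSIENT ISCHEMIC ATTACK, TIA | none |
| STROKE, ISCHEMIC STROKE, CVA | none |
| HYPERCHOLESTEROLEMIA | none |
| ISCHEMIC HEART DISEASE | HEART DISEASE |

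The first four rows fail for simple reasons. AGINA lacks the first N of ANGINA. HYPERCHOLESTEREMIA lacks the OL of the correct word, and HYPERCHOLESTOLEMIA lacks its ER, so neither is a substring of it. STROKE is absent from the list. The last row shows that the list catches some related wording.

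**Step 2. Terms that should not match**

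| Reported term | Counted as | Through keyword |
|---|---|---|
| HYPERGLYCEMIA | hyperlipidemia | HYPERGLYCEMIA |
| VAGINAL CANDIDIASIS, VAGINAL BLEEDING | cardiovascular disease | AGINA |

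**Step 3. Sensitivity to the matching rule.** If the program matches whole words instead of substrings, the VAGINAL matches disappear. The non-matches in Step 1 and the HYPERGLYCEMIA match remain.

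**Step 4. Size.** One misclassified subject moves a percentage by 1/55 = 1.8 points. For illustration only, 3 net misclassified subjects would move it by 3/55 = 5.5 points and 5 by 5/55 = 9.1 points. These numbers of subjects are assumptions, and zero is also possible. The B/F/TAF set is a subset of the 55, so the shift per subject there is at least 1.8 points; its size is not given. If it were 10 to 30 (assumption), one subject would be 1/30 = 3.3 to 1/10 = 10 points.

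**Step 5. Reach.** SAP 3.3 uses no covariates, 3.4 plans no subgroup analyses, and 3.5 states that there is no formal testing. The cardiovascular event listing (8.3.7.3) is driven by Appendix 4. The lipid sensitivity analyses (8.4.3) exclude subjects by statin use. None of these uses item 9's classification of history.

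**The case against.** The strongest defense is that the list may have been built from what sites actually wrote. Medical history is collected at screening, and the SAP was signed in December 2019, after the Week 24, 48 and 96 analyses. Two different misspellings of one word, together with informal phrases such as ARTERY BLOCKAGE, look like entries copied from the database. If so, a correct spelling may be absent because no subject had it, and the misses could be zero. The documents neither confirm nor exclude this, so nobody can say from them that the printed counts will be wrong. It does not rescue the rule, however. A glucose term in the lipid column is wrong whatever the sites wrote. A list tied to entered text is also fragile: a data query that corrects AGINA to ANGINA turns a match into a non-match.

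Second, the effect is small. These are descriptive rows, medical history is also listed by subject, and a subject missed on one term may be caught by another. That stands, and it sets the severity.

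Several stronger readings are tempting, and the documents do not support them:

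- **That these histories are undercounted.** The lists err both ways, so the net direction is unknown.
- **That hypertension has the same fault.** Its two keywords are correctly spelled, and item 9 adds the Adverse Event eCRF as a second source.
- **That the protocol itself defines cardiovascular disease to include the missed terms.** Protocol 6.2.1 does name "myocardial infarction, stroke, peripheral vascular/arterial disease, and/or angina", but as the scope of family history, not the subject's own. It cannot serve as the definition for this row.
- **That a large fraction of hyperlipidemia is lost.** No document gives its prevalence or the wording of the entries, so any such percentage would be invented.

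**Conclusion.** The point holds, as a minor one. As written, item 9 can misclassify baseline cardiovascular disease and hyperlipidemia in both directions. It misses correctly spelled angina, transient ischemic attack, stroke and hypercholesterolemia. It counts hyperglycemia as hyperlipidemia and, under substring matching, vaginal terms as cardiovascular disease. The consequence is confined to the descriptive baseline table of SAP 5.2, at 1.8 points per misclassified subject in the 55-subject set.

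The conclusion assumes that the keywords are applied to the reported terms as printed and without manual review, since the SAP describes none. It does not assume that any particular subject is misclassified.

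**What to change.** Replace the cardiovascular and hyperlipidemia columns of item 9 with a preferred-term list applied to the MedDRA-coded medical history. The medical monitor should review the list before database finalization, as Appendices 4 and 5 already do for events. The list should say explicitly whether it covers angina, transient ischemic attack, stroke and hypercholesterolemia.

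If the keyword method is kept, the minimum is to:

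1. add the correct spellings of angina, transient ischemic attack and hypercholesterolemia, and add STROKE;
2. remove HYPERGLYCEMIA from the lipid column;
3. replace AGINA, or restrict it to whole words, so that it cannot match VAGINAL;
4. compare both matches and non-matches with the coded history and record the result.

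The cost is one term list, a short medical review and a program change. No new data are needed.

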Appendix Table 6. ARV Category

Pre-ARV Categories	CMTRT3	ABBR	INGRED
TDF containing ARV	NRTI/INI: Stribild (EVG+COBI+FTC+TDF)	STB	EVG COBI FTC TDF
	NRTI/NNRTI: Atripla (EFV+FTC+TDF)	ATR	EFV FTC TDF
	NRTI/NNRTI: Complera (FTC+RPV+TDF)	CPA	FTC RPV TDF
	NRTI: Tenofovir DF (TDF)	TDF	TDF
	NRTI: Truvada (FTC+TDF)	TVD	FTC TDF
COBI/RTV/RPV containing ARV	NRTI/INI: Stribild (EVG+COBI+FTC+TDF)	STB	EVG COBI FTC TDF
	NRTI/NNRTI: Complera (FTC+RPV+TDF)	CPA	FTC RPV TDF
	NNRTI: Rilpivirine (RPV)	RPV	RPV
	PI: Kaletra (LPV+RTV)	LPV/r	LPV RTV
	PI: Ritonavir (RTV)	RTV	RTV
	Other	COBI	COBI
ABC containing ARV	NRTI: Abacavir (ABC)	ABC	ABC
	NRTI: Epzicom/Kivexa (ABC+3TC)	EPZ	ABC 3TC
	NRTI: Trizivir (ABC+AZT+3TC)	TZV	ABC AZT 3TC
FTC containing ARV	NRTI/INI: Stribild (EVG+COBI+FTC+TDF)	STB	EVG COBI FTC TDF
	NRTI/INI: Genvoya (EVG+COBI+FTC+TAF)	E-C-F-TAF	EVG COBI FTC TAF
	NRTI/NNRTI: Atripla (EFV+FTC+TDF)	ATR	EFV FTC TDF
	NRTI/NNRTI: Complera (FTC+RPV+TDF)	CPA	FTC RPV TDF
	NRTI: Emtricitabine (FTC)	FTC	FTC
	NRTI: Truvada (FTC+TDF)	TVD	FTC TDF
3TC containing ARV	NRTI: Lamivudine (3TC)	3TC	3TC
	NRTI: Epzicom/Kivexa (ABC+3TC)	EPZ	ABC 3TC
	NRTI: Trizivir (ABC+AZT+3TC)	TZV	ABC AZT 3TC
	NRTI: Combivir (AZT+3TC)	CBV	AZT 3TC
FTC containing ARV	NRTI/INI: Stribild (EVG+COBI+FTC+TDF)	STB	EVG COBI FTC TDF

13) Last Dose Dates and Last Study Date:

- a) Last Dose Date is defined in SAP Section 3.8.1. If the last dose date is incomplete or missing, the last dose date will be imputed as follows, using E/C/F/TAF or B/F/TAF dosing information as appropriate:
 - If the last dose date is missing day (ie, month and year of the last dose are known), the latest of dispensing dates of study drug bottles, study drug start dates and end dates, and imputed last dose date (day imputed as 15) will be used to impute the last dose date. However, if the month of the dispensing date is after the month of the last dose date, data query is needed. If subject died and the death date is complete (ie, not partial date) and before the imputed last dose date, the complete death date should be used as the imputed last dose date.
 - If the last dose date is missing day and month or completely missing (eg, due to lost to follow-up), the latest of study drug start dates and end dates, clinical visit dates, and laboratory visit dates (excluding the date of 30-day follow-up visit date) will be used to impute the last dose date.
- b) Last Study Date is the maximum of nonmissing study drug start dates and end dates, clinic visit and laboratory visit dates, including the 30-day follow-up visit date for subjects who prematurely discontinued study or who completed study according to study completion eCRF. Please note: if study drug start date or end date is partially missing, the imputed date (day imputed as 15) will be used. If subject died and the death date is complete (ie, not partial date) and before the imputed last study date, the complete death date should be used as the imputed last study date. Note that last visit date and last lab date include the 30-day follow-up visit.

14) Toxicity Grades:

- a) With regards to Triglycerides and Hypercholesterolemia, if the fasting status is not 'Y', in other words it is blank or 'N', then the lab result value would not be graded as non-fasting values are not interpretable.
- b) For toxicity grade summary, we will include all postbaseline graded results up to 30 days after the last dose of study drug, not just those at summarized visits.

15) Clarification of the following LOCF algorithms:

- Baseline values will not be carried forward.
- For CD4: If a value is missing in an analysis visit window, replace the missing value with the last on-treatment value observed before the analysis visit window that has the missing value.

16) For safety ECGs at postbaseline visits, the most conservative (worst) value within the window will be selected, eg, abnormal will be selected over normal for safety ECG or clinically significant abnormal will be selected over not clinically significant normal if there are multiple abnormal findings.

17) Treatment-Emergent Adverse Events

Events with Missing Onset Day and/or Month

The event is treatment emergent for the E/C/F/TAF phase if the following 3 criteria are met:

- The month and year (or year) of onset date is the same as or after the month and year (or year) of the first dose of E/C/F/TAF study drug, and
- The month and year (or year) of the onset date is the same as or before the month and year (or year) of the date corresponding to the minimum of (1) the last dose of E/C/F/TAF study drug plus 30 days AND (2) the first dose of B/F/TAF study drug minus 1 day, and
- End date is as follows:

The (complete) end date is on or after the first E/C/F/TAF dose date, or

The month and year (or year) of end date is the same or after the month and year (or year) of the first dose of E/C/F/TAF study drug, or

End date is completely missing

The event is treatment emergent for the B/F/TAF OL extension phase if the following 3 criteria are met:

- The month and year (or year) of onset date is after the month and year (or year) of the first dose of B/F/TAF study drug, and
- The month and year (or year) of the onset date is the same as or before the month and year (or year) of the date corresponding to the last dose of B/F/TAF study drug plus 30 days, and
- End date is as follows:

The (complete) end date is on or after the first B/F/TAF dose date, or

The month and year (or year) of end date is the same or after the month and year (or year) of the first dose of B/F/TAF study drug, or

End date is completely missing

Events with Completely Missing Onset Date

An AE with a completely missing onset date is defined as TEAE for the E/C/F/TAF phase if end date is as follows:

- The (complete) end date is on or after the first E/C/F/TAF dose date, or
- The month and year (or year) of end date is the same or after the month and year (or year) of the first dose of E/C/F/TAF study drug, or
- End date is completely missing

18) Calculation of ratios

To calculate laboratory ratios (eg, fasting total cholesterol to HDL ratio), lab value of each test in the ratio needs to be from the same accession number; if any test value used for the ratio calculation from the same accession number is missing, the ratio is not calculable (ie, missing).

19) Graded Laboratory Abnormalities Summary

The following labels will be used for treatment-emergent laboratory abnormalities and treatment-emergent Grade 3 or 4 laboratory abnormalities summary tables and listings:

Battery	Lab Test Label Used in l-labtox Listing	Toxicity Direction	Lab Test Label Used in t-labtox Table
Hematology	Hemoglobin	Decrease	Hemoglobin (Decreased)
	Neutrophils	Decrease	Neutrophils (Decreased)
	Platelets	Decrease	Platelets (Decreased)
	WBC	Decrease	WBC (Decreased)
Chemistry	Albumin	Decrease	Albumin (Decreased)
	Alkaline Phosphatase	Increase	Alkaline Phosphatase (Increased)
	ALT	Increase	ALT (Increased)
	Amylase	Increase	Amylase (Increased)
	AST	Increase	AST (Increased)
	Bicarbonate	Decrease	Bicarbonate (Decreased)
	Corrected Calcium	Increase	Corrected Calcium (Hypercalcemia)
	Corrected Calcium	Decrease	Corrected Calcium (Hypocalcemia)
	Creatine Kinase (CK)	Increase	Creatine Kinase (Increased)
	Creatinine	Increase	Creatinine (Increased)
	GGT	Increase	GGT (Increased)
	Lipase	Increase	Lipase (Increased)
	Magnesium	Decrease	Magnesium (Hypomagnesemia)
	Phosphate	Decrease	Phosphate (Hypophosphatemia)
	Serum Glucose (Fasting)	Increase	Serum Glucose (Fasting, Hyperglycemia)

Battery	Lab Test Label Used in l-labtox Listing	Toxicity Direction	Lab Test Label Used in t-labtox Table
	Serum Glucose (Fasting)	Decrease	Serum Glucose (Fasting, Hypoglycemia)
	Serum Glucose (Nonfasting)	Increase	Serum Glucose (Nonfasting, Hyperglycemia)
	Serum Glucose (Nonfasting)	Decrease	Serum Glucose (Nonfasting, Hypoglycemia)
	Serum Potassium	Increase	Serum Potassium (Hyperkalemia)
	Serum Potassium	Decrease	Serum Potassium (Hypokalemia)
	Serum Sodium	Increase	Serum Sodium (Hypernatremia)
	Serum Sodium	Decrease	Serum Sodium (Hyponatremia)
	Total Bilirubin	Increase	Total Bilirubin (Hyperbilirubinemia)
	Total Cholesterol (Fasting)	Increase	Total Cholesterol (Fasting, Hypercholesterolemia)
	Triglycerides (Fasting)	Increase	Triglycerides (Fasting, Increased)
	LDL (Fasting)	Increase	LDL (Fasting, Increased)
	Urea Nitrogen (BUN)	Increase	Urea Nitrogen (Increased)
	Uric Acid	Increase	Uric Acid (Hyperuricemia)
	Uric Acid	Decrease	Uric Acid (Hypouricemia)

20) Concomitant nonstudy-drug ARV medications (ie, ARV medications other than study drug that are taken while receiving study drug) will be flagged in “Nonstudy-Drug Antiviral Medication” listing. The logic to define concomitant nonstudy-drug ARV is similar to concomitant non-ARV Medications (see details in Section 8.6.2)

21) Lipid modifying medication analyses:

- Lipid modifying medication is defined to be the concomitant medication with ACLAS “LIPID MODIFYING AGENTS” and CMDECOD contains wording of “STATIN” in the ADCM dataset.
- Subjects who took lipid modifying medications at study entry refer to the subjects who have any use of the lipid modifying agents at study day 1 (ie, the first E/C/F/TAF dose date).
 - a) More specifically, subjects with “Lipid Modifying Agent Use at Study Entry” include those subjects in E/C/F/TAF Safety Analysis set meeting both the following criteria:
 - 1) any selected CM record with the start date \leq the first E/C/F/TAF dose date, and
 - 2) the end date of the selected CM record \geq the first E/C/F/TAF dose date or the end date of the selected CM record is ongoing
 - b) For lipid modifying medications with the start date completely unknown, we assume the start date is on or before the E/C/F/TAF first dose date, lipid modifying medication was considered as being taken at study entry if the end date is not prior to the first E/C/F/TAF dose date (ie, the end date is on or after the first E/C/F/TAF dose date, completely unknown, or ongoing).

- c) Lipid modifying medications with the start date prior to the first E/C/F/TAF dose date and the end date unknown (completely missing) were considered as being taken at study entry (the unknown end date is assumed on or after the first E/C/F/TAF dose date).
- Subjects who initiated lipid modifying medications during the E/C/F/TAF phase refers to the subjects in the E/C/F/TAF Safety Analysis set who did not take lipid modifying medications at study entry and met the following criteria: 1) any selected CM record started after the first E/C/F/TAF dose date and on and prior to the last E/C/F/TAF dose date.
- Subjects who took lipid modifying medications at the start of the B/F/TAF OL extension phase refer to the subjects who have any use of the lipid modifying agents at B/F/TAF Study Day 1 (ie, the first B/F/TAF dose date).
- d) More specifically, subjects with “Lipid Modifying Agent Use at Entry in B/F/TAF OL Extension Phase” include those subjects in the B/F/TAF Safety Analysis set meeting both the following criteria: 1) any selected CM record with the start date \leq the first B/F/TAF dose date, and 2) the end date of the selected CM record \geq the first B/F/TAF dose date or the end date of the selected CM record is ongoing
- e) For lipid modifying medications with the start date completely unknown, we assume the start date is on or before the B/F/TAF first dose date, lipid modifying medication was considered as being taken at start of B/F/TAF OL extension phase if the end date is not prior to the first B/F/TAF dose date (ie, the end date is on or after the first B/F/TAF dose date, completely unknown, or ongoing).
- f) Lipid modifying medications with the start date prior to the first B/F/TAF dose date and the end date unknown (completely missing) were considered as being taken at the start of the B/F/TAF OL extension phase (the unknown end date is assumed on or after the first B/F/TAF dose date).
- Subjects who initiated lipid modifying medications during the B/F/TAF OL extension phase refers to the subjects in the B/F/TAF Safety Analysis set who did not take lipid modifying medications at the start of the B/F/TAF OL extension phase and met the following criteria: 1) any selected CM record started after the first B/F/TAF dose date and on and prior to the last B/F/TAF dose date.

22) For figures, if at a visit where n (sample size) for any treatment group ≤ 5 , data for that treatment group will not be displayed at the visit in figure (except the Kaplan-Meier figure), but all data will be included in the corresponding table summary.

23) LDL: Conversions between 2nd and 3rd generations

LDL was analyzed by 2 different assays in the study: 2nd generation (RCT2394) and 3rd generation (RCT3870). Samples collected at earlier visits were analyzed using LDL 2nd generation assay. Samples collected at later visits were analyzed using LDL 3rd generation assay. The conversion formulas are as follow:

$$\text{2nd Gen (mmol/L)} = (\text{3rd Gen} - 0.0626)/0.882$$

$$\text{3rd Gen (mmol/L)} = (0.882 \times \text{2nd Gen}) + 0.0626$$

For this analysis, since LDL samples were analyzed by 2nd generation assay at Baseline, only conversion from 3rd generation to 2nd generation will be performed.

For the analysis of change from baseline in fasting direct LDL: the sample analyzed by LDL 3rd generation assay will be converted to 2nd generation as a new record with test codes of LIP.LDL.00.02 in raw data. During ADaM stage, a derived parameter code (FLDL2) for “Fasting LDL Cholesterol 2ND GEN Combined” will be generated to pool the records from both original and converted (LIP.LDL.00.02) 2nd generation results to calculate the change from baseline in fasting direct LDL.

For the analysis of toxicity grade for fasting direct LDL: toxicity grade will be based on the Gilead grading results (ie, toxgrg) from the original values before conversion. In another words, during ADaM programming stage, a derived parameter code (FLDLTOX) for “Fasting LDL Cholesterol for Toxicity” will be generated to pool the records from 2nd generation and 3rd generation to derive treatment-emergent toxicity grades, maximum postbaseline toxicity grades, etc.

24) Plasma concentrations

During the B/F/TAF OL extension phase, at Weeks 4, 24, and 48, on the day of hemodialysis, a sparse timed blood sample was to be collected from all subjects within 10 minutes prior to hemodialysis initiation. Predose (within 30 minutes prior to study drug administration) blood draws for plasma samples were also collected at these visits. For the summary table, all values will be listed; however only trough values will be included in the summary statistics. Values not included in the summary statistics should be flagged.

In general, intensive PK concentration values that are BLQ will be treated as 0 at predose timepoints and one-half the value of the LLOQ at postdose time points for summary purposes. Other PK concentration values (including trough, predose, postdose, anytime PK concentration) that are BLQ will be treated as one-half of the LLOQ.

SAP Final GS-US-292-1825

ELECTRONIC SIGNATURES

Signed by	Meaning of Signature	Server Date (dd-MMM- yyyy hh:mm:ss)
PPD	Project Team Leader eSigned	03-Dec-2019 11:13:38
PPD	Biostatistics eSigned	03-Dec-2019 17:27:06
PPD	Project Team Leader eSigned	05-Dec-2019 01:44:24
